4.2 Scientific Rationale for Trial Design

The D-Tect Patch is a new generation patch that has been developed for use in the DMS. Predecessor patches used in conjunction with the DMS were tested for packet detection performance as well as detection latency. This trial is being conducted to demonstrate that the D-Tect Patch performance is comparable to predecessor patch data.

4.3 Dosing Rationale

In Cohort 1, no medication will be ingested.

In Cohort 2, subjects will ingest a single dose of Abilify MyCite (aripiprazole embedded with an IEM) at the same dose as their currently prescribed aripiprazole. The following doses of Abilify MyCite are available for use in this trial: 2 mg, 5 mg, 10 mg, 15 mg, 20 mg, and 30 mg. The dose of Abilify MyCite will be recorded in subject's source documentation and the electronic case report form (eCRF).

4.4 Start and End-of-Trial Definitions

The trial start is defined as the first visit of the first subject, which is the date the first subject signs their ICF.

The end-of-trial date is defined as the last date of contact, or the date of final contact attempt as recorded in subject's source documentation for the last subject completing or withdrawing from the trial.

4.5 Definition of Completed Subjects

The trial period is defined as the time period during which subjects are evaluated for the primary objective of the trial irrespective of whether or not the subject wears the patch or ingests all IEMs. Subjects who are evaluated at the last scheduled visit will be defined as trial completers.

5 Trial Population

Two cohorts of subjects will be enrolled in this trial.

Cohort 1: A minimum of 24 healthy subjects will be tested to obtain a minimum of 360 miniature IEM tablet ingestions for Cohort 1. Healthy subjects will be drawn from nonvulnerable subpopulations. If a subject fails to complete participation in the testing, for whatever reason, a new, qualified candidate may be enrolled as a replacement.

Cohort 2: A minimum of 30 subjects with SMI will be tested to obtain a minimum of 30 Abilify MyCite ingestions for Cohort 2. Subjects will ingest Abilify MyCite at the same dose as their currently prescribed aripiprazole. If a subject fails to complete

Confidential - Proprietary Information

participation in the testing, for whatever reason, a new, qualified candidate may be enrolled as a replacement.

5.1 Subject Selection and Numbering

All subjects will be given a unique subject identifier (ID; site number [3 digits] + subject number ['S' + 5 digits] upon providing consent). The site number will be designated by the sponsor. The subject number will be given sequentially from S00001.

Demographic information (date of birth, sex at birth, gender identification, childbearing potential, race, ethnicity) and medical history will be recorded in the eCRF at the screening visit.

5.2 Eligibility Criteria

Exceptions for eligibility criteria will not be permitted during the trial, neither by the investigator nor by the sponsor.

5.2.1 Inclusion Criteria

Subjects are required to meet the inclusion criteria shown in Table 5.2.1-1 to participate in Cohort 1 of the trial:

| De 5.2.1-1 Inclusion Criteria (Cohort 1) |
|--|
| Have read, reviewed with trial site staff, and signed the informed consent. |
| Male or female at least 18 years of age. |
| In good general health or medically stable. |
| Is able and willing to participate in, and adhere to, all testing procedures, both onsite and offsite, |
| for the entire testing. |
| Subject has access to a telephone for communicating with the trial personnel and for trial personnel to contact the subject. |
| |

Subjects are required to meet the inclusion criteria shown in Table 5.2.1-2 to participate in Cohort 2 of the trial:

| Ta | ble 5.2.1-2 Inclusion Criteria (Cohort 2) |
|----|--|
| 1. | Have read, reviewed with trial site staff, and signed the informed consent. |
| 2. | Male or female at least 18 years of age. |
| 3. | In good general health or medically stable. |
| 4. | Has confirmed diagnosis of Schizophrenia, Major Depressive Disorder, or Bipolar I Disorder per |
| | Diagnostic and Statistical Manual of Mental Disorders - 5th Edition (DSM-5) criteria and currently |
| | prescribed and taking aripiprazole. |
| 5. | Is able and willing to participate in, and adhere to, all testing procedures, both onsite and offsite, |
| | for the entire testing. |
| 6. | Subject has access to a telephone for communicating with the trial personnel and for trial personnel to contact the subject. |

5.2.2 **Exclusion Criteria**

Subjects will be excluded from Cohort 1 and/or Cohort 2 if they meet any of the exclusion criteria shown in Table 5.2.2-1:

| Ta | ble 5.2.2-1 Exclusion Criteria (Cohort 1 and Cohort 2) |
|----|---|
| 1. | Any medical condition, treatment, or symptoms that, in the judgment of the trial clinician, could place the subject at more than the minimal risk from involvement in the testing. |
| 2. | Hospitalization, emergency room visit, surgery or new medical treatment within 30 days before testing begins or planned during testing. |
| 3. | Difficulty with or inability to swallow tablets. |
| 4. | Active skin infection or active dermatitis, OR history of chronic inflammatory skin condition including psoriasis and chronic dermatitis (except atopic dermatitis). |
| 5. | The investigator will determine if any subject should be excluded from the trial based on history of, OR current, alcohol abuse, drug abuse or use of illegal drugs (eg, amphetamines or heroin). |
| 6. | Allergy to adhesive bandages/tapes (eg, Band-Aids®) or latex. |
| 7. | Positive urine pregnancy test at screening visit (dipstick). |
| 8. | Subject is taking any concomitant medication that places the subject at a greater risk for skin reactions or skin sensitivity. |

A definition of childbearing potential can be found in Section 10.2.

5.3 Lifestyle Considerations

Not applicable.

5.4 Screen Failures

A screen failure is a subject from whom informed consent is obtained and is documented in writing (ie, subject signs an ICF), but who does not have a patch applied. All AEs must be reported after subject informed consent has been obtained, including screen failures due to AEs, irrespective of trial intervention administration.

If the subject meets the definition of a screen failure in this trial, the following information will be recorded in the eCRF:

- Date of ICF signature •
- Visit date (screening visit) •
- Demographics •
- Result of eligibility assessment •
- Screen failure date •
- Reason for screen failure •
- Any AEs •

Individuals who do not meet the criteria for participation in this trial (screen failure) may not be rescreened.

Confidential - Proprietary Information

23

6 Trial Device(s) and Concomitant Therapy

6.1 Trial Device(s) Administered

Trial devices intended to be administered to the subjects during the conduct of the trial are listed in Table 6.1.1-1.

For information regarding the dose and observation period(s), including any follow-up period for the trial, see Section 4.1.

6.1.1 **Medical Devices**

The system components used in this trial are shown below in Table 6.1.1-1.

| Table 6.1.1-1System Comp | | ponents to be Tested |
|--------------------------|-----------------------------|--|
| Cohort | System Component | Description |
| Cohort 1 | MIT (placebo embedded with | The MIT formulation is an IEM inside an inert tablet which |
| | an IEM) | will be dispensed to subjects to be ingested 15 times in |
| | | 1 day during the trial. |
| Cohort 2 | Abilify MyCite tablet | The Abilify MyCite formulation is an IEM inside an |
| | (aripiprazole embedded with | aripiprazole tablet which will be dispensed to subjects to be |
| | an IEM) | ingested one time during the trial. |
| Cohorts | D-Tect Patch | A D-Tect Patch will be applied by clinic staff prior to |
| 1 and 2 | | DOIs. |
| Cohorts | Computerized Device and | A computerized device (eg, smart phone) and accessories |
| 1 and 2 | Accessories | will be used by the clinic staff to track IEM detection on the |
| | | software application. |

| Table 6.1.1-1 | System Components to be Tested |
|---------------|--------------------------------|
| | |

6.2 Management of Trial Device

For full details on management of trial device(s), please refer to the trial-specific operations manual.

6.2.1 Packaging and Labeling

The D-Tect Patches will be provided by the sponsor or designated agent to the site. The D-Tect Patches will be supplied in pouches. Each patch used will be labeled to clearly disclose the unique patch serial number (SN) and lot number. The SN and lot number will be recorded in the eCRF.

The IEMs (MITs and Abilify MyCite) will be provided by the sponsor or designated agent to the investigators and the persons designated by the investigator(s) or institution(s). The MITs and Abilify MyCite will be supplied in bottles. For Abilify MyCite, 1 bottle of each dose will be supplied to the site.

Confidential - Proprietary Information

24

6.2.2 Storage

The device and components (ie, patches and IEMs [MITs and Abilify MyCite]) will be stored in a securely locked cabinet or enclosure. MITs and Abilify MyCite must be stored in a secure, environmentally controlled, and monitored (manual or automated) area in accordance with the labeled storage conditions with access limited to the investigator and authorized site staff.

6.2.3 Accountability

The investigator or designee must maintain an inventory record of the D-Tect Patches, IEMs (MITs and Abilify MyCite), and mobile device(s) received, dispensed, administered, returned, and lost (if applicable). Neither the investigator nor any designees may provide a device to any subject not participating in this trial.

6.2.4 Returns and Destruction

The mobile devices will be returned to the sponsor representatives after completion of all ingestions on Day 1.

The D-Tect Patches will be collected by the sponsor representatives after accountability. Upon completion or termination of the trial, all used and unused D-Tect Patches must be returned to the sponsor or a designated agent. All D-Tect Patches returned to the sponsor must be accompanied by the appropriate documentation and be clearly identified by protocol number and trial site number on the outermost shipping container. Returned D-Tect Patches should be in the original containers and used patches should be stuck to the inside of a zip lock bag. The assigned trial monitor will facilitate the return of used and unused D-Tect Patches.

Tablets (MITs and/or Abilify MyCite) may be returned to the sponsor and/or destroyed by the clinical trial site following completion and verification of accountability. Refer to the Pharmacy Manual for instructions on returns and/or destruction.

6.2.5 Reporting of Product Quality Complaints

Product Quality Complaints (PQCs) will be reported for Abilify MyCite tablets only. PQCs will not be reported for the D-Tect Prototype Patch, MIT dose form, or app.

A PQC is any written, electronic, or oral communication provided by a healthcare professional, consumer, clinical trial subject, medical representative, regulatory agency, partner, or other third party that alleges deficiencies related to the identity, quality, durability, reliability, safety, effectiveness, or performance of a medical device or

medicinal product or a falsified, tampered, or diverted product after it is released for distribution.

Examples include, but are not limited to, communications involving:

- Failure of a product to meet any of its specifications.
- Incorrect or missing labeling.
- Packaging issues: (eg, damaged, dirty, crushed, missing tablet, missing patch/pod, missing component).
- Tablet/bottle defects: (eg, odor, under-filled bottle, empty bottle, over-filled bottle, tablet not registering with the app, chipped tablet, broken tablet).
- Loss or theft of product.

6.2.5.1 Eliciting and Reporting Product Quality Complaints

The investigator or designee must record each PQC identified through any means from the receipt of the Abilify MyCite tablets from the sponsor or sponsor's designee, through and including reconciliation and up to destruction, including subject dosing. The investigator or designee must notify the sponsor (or sponsor's designee) within 24 hours of becoming aware of the PQC according to the procedure outlined below.

Send PQC reporting information to the OPDC IMP complaints mailbox email:

Email: [contact]

Also indicate whether or not the complaint sample is available for return.

Identification of a PQC by the subject should be reported to the site investigator, who should then follow the reporting mechanism above.

6.2.5.2 Information Required for Reporting Purposes

- Description of complaint
- Reporter identification (eg, subject, investigator, site, etc)
- Reporter contact information (eg, address, phone number, email address)
- Subject number
- Clinical site number
- ID of material (product/compound name, lot/batch number, shipment number, expiry date)
- Clinical protocol reference (number and/or trial name)
- Dosage form/strength (if known)
- Pictures of complaint sample (if available)
- Availability of complaint sample for return

Confidential - Proprietary Information

26

6.2.5.3 Return Process

Indicate during the report of the PQC if the complaint sample is available for return.

If the complaint sample is available for return, the return instructions will be provided by the sponsor.

It must be documented in the site accountability record that the complaint sample has been forwarded to the sponsor for complaint investigation.

6.2.5.4 Assessment/Evaluation

Assessment and evaluation of PQCs will be handled by the sponsor.

6.3 Measures to Minimize/Avoid Bias

This is an open-label trial.

6.4 Subject Compliance

A subject will be withdrawn from the trial by the investigator (or designee) if the subject is noncompliant with the protocol (defined as refusal or inability to adhere to the trial schedule or procedures) and the details will be recorded on the appropriate eCRF.

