2.3.1.2 Allergic Reaction

An allergic reaction could potentially arise from exposure to components of the patch adhesive.

To mitigate the risk of this potential hazard, prospective subjects who have a known allergy to skin adhesives will be excluded from the trial. Allergy to bandages, tapes, and latex will be specifically queried.

Subjects will be told that they are free to remove the patches at any time and to inform the clinical research site immediately. Subjects will also be told to reach out for emergency medical care should they have immediate need for medical attention.

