7.3 Discontinuation of Trial Device

Under certain circumstances, it may be necessary for a subject to permanently discontinue the trial. If trial IEMs or patches are permanently discontinued, the subject should, if at all possible, remain in the trial to be evaluated for safety assessments. See the schedule of assessments (SoA) for data to be collected at the time of discontinuation of trial device and follow-up and for any further evaluations that need to be completed. If a subject discontinues the trial due to an AE, the investigator, or other trial personnel, will make every effort to follow the event until it has resolved or stabilized.

For each subject who discontinues the trial, the main reason for discontinuation will be recorded in the eCRF (refer to Section 7.4.1).

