7.4 Subject Discontinuation/Withdrawal from the Trial

- A subject may withdraw from the trial at any time at the subject's own request for any reason (or without providing any reason).
- A subject may be withdrawn at any time at the discretion of the investigator for safety, behavioral, or compliance reasons.

Confidential - Proprietary Information

28

- At the time of discontinuing from the trial, if possible, an early discontinuation visit should be conducted to assess any new or ongoing AEs.
- If a subject withdraws consent from the trial, the subject will be permanently discontinued from all trial procedures and the trial.
- If the subject withdraws consent for disclosure of future information, the sponsor may retain and continue to use any data collected before the withdrawal of consent.

Complete withdrawal of consent requires a subject's refusal of ALL of the following methods of follow-up:

- Participation in all follow-up procedures specified in the protocol (whether in-clinic, by telephone, or by a home visit).
- Participation in a subset of protocol-specified follow-up procedures (by a frequency schedule and method, as agreed by subject and trial site staff).
- Contact of the subject by trial site staff, even if only by telephone, to assess current medical condition, and obtain necessary medical reports relevant to the trial's objectives.
- Contact of alternative person(s) who have been designated in source records as being available to discuss the subject's medical condition, even if only by telephone, mail, or email (eg, family, spouse, partner, legal representative, friend, neighbor, or physician).
- Access to medical information from alternative sources (eg, hospital/clinic medical records, referring doctor's notes, public records, dialysis, transplantation or vital registries, social media sources).

Withdrawal of consent is a critical trial event and, therefore, should be approached with the same degree of importance and care as is used in initially obtaining informed consent. The reasons for a subject's intended withdrawal need to be completely understood, documented, and managed to protect the rights of the subject and the integrity of the trial. Only subjects who withdraw their permission for all of the above methods of follow-up are considered to have completely withdrawn their consent to participate in the trial.

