10.1.6 Protocol Deviations

In the event of a significant/major deviation from the protocol due to an emergency, accident, or mistake (eg, violation of informed consent process, trial device dispensing or subject dosing error, subject enrolled in violation of eligibility criteria or concomitant medication criteria), the investigator or designee will contact the sponsor or designee at the earliest possible time by telephone or via email. The investigator and sponsor (or designee) will come as quickly as possible to a joint decision regarding the subject's continuation in the trial. This decision will be documented by the investigator and the sponsor (or designee) and reviewed by the site monitor.

Any major protocol deviation will be recorded in the eCRF along with the start date and details of the deviation.

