12.1 Subject Disposition

The following information will be summarized for subject disposition by cohort in table based on **SCR** Analysis Set:

• Number and percentage of subjects screened,

Page 12 of 20

Strictly Confidential. © 2023, PRA Health Sciences. All rights reserved.

- Number and percentage of screening failures and corresponding reasons for screening failure,
- Number and percentage of subjects included in each analysis set (EAS, FAS, and SAF).

Furthermore, following information will be provided by cohort in tables based on EAS.

- Number and percentage of subjects who complete all the ingestions,
- Number and percentage of subjects who complete study,
- Number and percentage of discontinuations from study and corresponding reasons for discontinuation,

The following reasons - as specified in the CRF - will be included in the disposition tables and in a listing (Listing: Enrollment and Study Completion for **SCR** Analysis Set):

Reasons for Screening Failure:

- 1. Failed Inclusion Criteria
- 2. Met Exclusion Criteria
- 3. Death
- 4. Adverse Event
- 5. Physician Decision
- 6. Pregnancy
- 7. Protocol Deviation
- 8. Terminated by Sponsor
- 9. Withdrawal by Subject
- 10. Other

Reasons for Study Discontinuation:

- 1. Death
- 2. Adverse Event
- 3. Lost to Follow-up
- 4. Non-compliance with Device/Patch
- 5. Physician decision
- 6. Pregnancy
- 7. Protocol Deviation
- 8. Terminated by Sponsor
- 9. Withdrawal by Subject
- 10. Withdrawal of Consent

Strictly Confidential. © 2023, PRA Health Sciences. All rights reserved.

11. Other

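### Protocol 6.4 makes trial withdrawal mandatory for noncompliance, out of step with the discretion in 7.4 and, where ingestions or the patch are stopped, with the retention for safety in 7.3

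*Protocol*

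**What the plan says.** Three Protocol sections bear on a subject who stops following the plan.

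- **6.4 Subject Compliance:** "A subject will be withdrawn from the trial by the investigator (or designee) if the subject is noncompliant with the protocol". Noncompliance means refusal or inability to keep to the schedule or procedures. No degree of severity is set and no discretion is given.
- **7.4 Subject Discontinuation/Withdrawal from the Trial:** "A subject may be withdrawn at any time at the discretion of the investigator for safety, behavioral, or compliance reasons".
- **7.3 Discontinuation of Trial Device:** when tablets or patches are permanently stopped, "the subject should, if at all possible, remain in the trial to be evaluated for safety assessments".

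Two further places determine how such a subject is reported. Protocol 4.5 states: "Subjects who are evaluated at the last scheduled visit will be defined as trial completers". SAP 12.1 tabulates, on the Enrolled Analysis Set, "Number and percentage of subjects who complete study", together with discontinuations and their reasons. One of the listed reasons is noncompliance with the device or patch.

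**The concern.** Stopping a study procedure and leaving the trial are different events, and 6.4 turns the first into the second. A Cohort 1 subject who cannot swallow the rest of the 15 tablets, but is willing to return on Day 8, must be withdrawn under 6.4 and should if possible be kept under 7.3. An investigator who keeps that subject departs from 6.4. One who withdraws the subject departs from the preference in 7.3. No text says which section governs.

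At stake is the only secondary endpoint, adverse events. Visit 3 is the one scheduled adverse event assessment after the testing visit, and it is where the site is photographed and the patch removed. Protocol 2.3.1.1 expects that irritation may come from wearing the patch or from taking it off, so Visit 3 is the natural point to see it.

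**Working it through.** The documents give no figure to reproduce on this point. The check is a comparison of text, followed by simple bounds on the effect.

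**1. The rules side by side**

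| Section | Trigger | Consequence | Force |
|---|---|---|---|
| 6.4 | Refusal or inability to follow schedule or procedures | Withdrawal from the trial | Mandatory |
| 7.4 | Safety, behavioral or compliance reasons | Withdrawal from the trial | Investigator's discretion |
| 7.3 | Tablets or patch permanently stopped | Stay for safety assessments | Preferred, where possible |

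Sections 6.4 and 7.4 share the compliance trigger and the consequence but differ in force. Sections 6.4 and 7.3 have different triggers, which overlap when the noncompliance consists of stopping the tablets or the patch. In that overlap the consequences are opposite.

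**2. Who is affected**

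- A subject who refuses Visit 3 itself cannot be kept for it under any wording.
- Taking the patch off is a doubtful case for 6.4, because Protocol 2.3.1.2 says "Subjects will be told that they are free to remove the patches at any time".
- Refusing remaining tablets can arise only in Cohort 1, since Cohort 2 takes one tablet.
- Refusing the daily Sleep Diary, listed among the subject's responsibilities in Protocol 8, can arise in both cohorts.

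The group is therefore subjects who decline or cannot do something other than Visit 3 and would still attend it.

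**3. Follow-up at stake** (Visit 3 on Day 8, +2 days)

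- To Day 8, for withdrawal on Day 1: 8 − 1 = 7 days.
- To the end of the window: 10 − 1 = 9 days.
- Later withdrawal costs less.

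**4. What other sections recover**

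- 7.4 asks for an early discontinuation visit, if possible. If it is held on Day 1, it cannot record an event that starts later.
- 8.7.2 has adverse events assessed to the end of the trial and followed to resolution, with no stated exception for withdrawn subjects. It sets no contact date for them.
- 8.7.7.2 monitors for serious events up to 7 (+2) days after patch application and ingestion.
- 7.3 follows an event that itself caused discontinuation, which noncompliance is not.

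What remains exposed is new non-serious events, mainly skin, that begin after the last contact.

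**5. Effect on the completion percentage**

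For one subject withdrawn who would otherwise have attended Visit 3, the fall is 1/N:

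- Cohort 1 at the minimum of 24: 1/24 = 4.2 points. With a replacement enrolled: 1/25 = 4.0.
- Cohort 2 at the minimum of 30: 1/30 = 3.3 points. With a replacement enrolled: 1/31 = 3.2.

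These are upper bounds per subject, because both cohort sizes are minimums.

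**6. Primary results**

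The SAP's Full Analysis Set (9.2.3) is built from detections in anyone who took at least one dose, so withdrawal does not remove ingestions already made. The Safety Analysis Set (9.2.4) needs only patch wear or a tablet plus any safety assessment.

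**The case against.** The best defence is that 6.4 and 7.4 can stand together. Section 7.4 is a general power, and 6.4 is a defined criterion inside it. Protocol 7.4.1 supports this by listing a met protocol-specific withdrawal criterion as a reason separate from a physician's decision. On that reading, withdrawing a subject under 6.4 breaches nothing in 7.4, lesser lapses stay discretionary, and whether someone is unable or refusing is still for the investigator to judge. This stands. A reader might infer that 6.4 and 7.4 flatly contradict each other, and the documents do not support so strong a claim. The defence does not, however, reach 7.3: a mandatory criterion that fires because tablets or patch were stopped still meets an instruction to keep that same subject if possible.

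A reader might also add two sections to the list of conflicts. Neither belongs there.

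- Under 10.1.6 the investigator and sponsor "will come as quickly as possible to a joint decision" on continuation, but only for significant or major deviations arising from an emergency, accident or mistake. Refusal is none of these.
- Section 4.5 defines the trial period "irrespective of whether or not the subject wears the patch or ingests all IEMs". That is a definition and sets no rule on retaining subjects. Its completer definition matters here only for how a withdrawn subject is counted.

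It is also fair to say that the loss is small. Section 7.4 treats consent as completely withdrawn only when every listed form of follow-up is refused, so contact after an investigator's withdrawal stays open. The safeguards in step 4 are real, and the Protocol describes the trial as minimal risk.

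**Conclusion.** The point holds as a wording problem with a limited practical effect. Section 6.4 is out of step with the discretion in 7.4, and in the overlap it pulls against 7.3 with nothing to reconcile them. The consequence is possible loss of up to 7 days (9 at the window's end) of scheduled assessment for new non-serious, mainly skin, events, and a change in how the subject is counted. It applies only to subjects who would have come to Visit 3.

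The completion figures rest on the minimum cohort sizes and on one affected subject, and they touch a descriptive table only. The documents give no expected number of such subjects and no adverse event rate, so no effect on adverse event counts can be stated. It would be wrong to infer that PDA, latency or the analysis sets are compromised, or that every missed procedure leads to withdrawal. This is worth considering, not a barrier to the trial.

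**What to change.** Replace the paragraph in 6.4 with text to this effect:

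> A subject who refuses or cannot follow the trial schedule or procedures may be taken off the patch, the remaining ingestions, or both. Wherever possible, that subject stays in the trial for the Day 8 (+2 days) safety assessment (Section 7.3). Withdrawal from the trial for noncompliance is at the investigator's discretion (Section 7.4). Details are recorded on the appropriate eCRF.

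Sections 7.3 and 7.4 need no change. The SAP's discontinuation reason for noncompliance also stays as it is, because it still applies to a discretionary withdrawal.

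The cost is one reworded paragraph, with no new visit, data item or analysis. The Protocol synopsis expects the whole trial to take about 24 days, so the change helps only if made before enrolment or early in it.
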